2.0 INTRODUCTION

Study RAP-MD-03 is a Phase 3, multi-center, randomized, double-blind, placebo-controlled, parallel-group study in patients who are 18 to 65 years of age, meet DSM-5 (Diagnostic and Statistical Manual of Mental Disorders, Fifth Edition) criteria for Major Depressive Disorder (MDD), have a minimum score of 25 on the Montgomery-Åsberg Depression Rating Scale (MADRS), and have an ongoing inadequate response to antidepressant therapy (ADT).

[figure not shown]
The study will consist of up to a 14-day screening and washout period followed by a 1-week placebo lead-in period, a 2-week randomized treatment period, and then a 1 week of safety follow-up period. Both the placebo lead-in period and randomized treatment period will be conducted in a double-blind (DB) manner. Consequently, the combination of these two periods is referred to as the DB treatment period.

[figure not shown]
Signed informed consent from the patient or the patient's legally authorized representative will be obtained before any study-related procedures are begun. At the end of the screening period, patients meeting the eligibility criteria for this study will be enrolled into a 1-week, double-blind, placebo lead-in period intended to identify placebo responders. Placebo responders will be defined by meeting at least 1 of the following criteria at any time point during the 1-week double-blind placebo lead-in:

[figure not shown]
- Patients with \geq 50% decrease from Day 0 MADRS total score
- Patients achieving a MADRS total score of \leq 14 points

Upon completion of the placebo lead-in period, patients will be randomized in 1:1 ratio to receive either rapastinel 450 mg or placebo, adjunctive to ongoing ADT. Randomization will be stratified by patient's responder status (as placebo non-responder vs. placebo responder) achieved during the end of the placebo lead-in period. The schedule of visits and procedures for study RAP-MD-03 is presented in [Table 2-1](#). The study design is shown graphically in [Figure 2-1](#).

This SAP provides a more technical and detailed elaboration of the statistical analyses of efficacy and safety data as outlined and/or specified in the final study Protocol Amendment 2 (version dated 20NOV2018) and the Restricted Access Addendum Amendment 2 (version dated 20NOV2018). Specifications of tables, figures, and data listings are contained in a separate document.

RES1

[figure not shown]

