5.0 PATIENT DISPOSITION

The number of patients in the Enrolled, Safety and mITT populations will be summarized by treatment group and by study center.

Screen-failure patients (ie, patients screened but not included in the enrolled population) and their associated reasons for failure to enroll will be tabulated overall for all screened patients.

The number and percentage of patients in the mITT population who complete the randomized treatment period, of patients who prematurely discontinue during the same period and who entered the safety follow-up period will be presented for each treatment group and pooled across treatment groups for placebo lead-in period responders and non-responders both separately and combined. The reasons for premature discontinuation during the randomized treatment period as recorded on the disposition pages of the electronic case report forms (eCRFs) will be summarized by treatment group and placebo lead-in period responder status for the mITT Population.

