8.0 EFFICACY ANALYSES

All efficacy analyses will be based on the mITT Population, unless stated otherwise. The baseline for each specific efficacy endpoint is defined as the last measurement prior to the first dose of randomized treatment. The Day 0 measure for each specific efficacy endpoint is defined as the last measurement prior to the first dose of double-blind IP in the placebo lead-in period. The analyses for the placebo lead-in period will be presented for all patients combined and separately for the placebo responders vs. non-responders using the Enrolled Population. All statistical hypothesis tests will be performed at the 2-sided 5% significance level for main effects. All confidence intervals (CIs) will be 2-sided 95% CIs, unless stated otherwise.

For efficacy analyses in which study center is a factor, a *small center* will be defined as a center with less than 2 placebo non-responder patients in at least 1 treatment group in the mITT Population. Small centers will be pooled to form pseudo-centers so that each treatment group includes at least 2 placebo non-responder patients within the center for the mITT population. Pooling will be done using the following algorithm:

Based on the number of placebo non-responder mITT patients, small centers will be ordered from the largest to the smallest, and centers of the same size will be ordered from the largest center number to the smallest center number. The pooling process starts with the largest small center from the top, which will be pooled with the smallest from the bottom until a non-small center is formed. The process will be repeated using the small centers left out after the first pass. If any centers are left out at the end of the process, they will be pooled with the smallest pseudo-center. If there is more than 1 smallest pseudo-center, the pseudo-center with the smallest center number will be selected. In case the pseudo-center formed by pooling all small centers is still a small center, it will be pooled with the smallest non-small center. If there is more than 1 smallest non-small center, the one with the smallest center number will be selected.

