If any, the centers with only placebo responder patients will be ordered from largest to the smallest by the number of patients. The smallest pooled center (based on placebo non-responder as defined in the previous paragraph) will be combined with largest center with only placebo responder patients; the second smallest pooled center (based on placebo non-responder as defined in the previous paragraph) will be combined with the second largest center with only placebo responder patients; the remaining centers with only placebo responder patients will be combined similarly. Centers with same number of patients will be further ordered by the center code.

The final pooled pseudo-centers will be used for all efficacy analyses when the model is adjusted for study center.

The efficacy analyses of MADRS assessments will be based on the rater-administered MADRS. The efficacy analyses using the mITT population will be performed based on the treatment to which the patient is randomized regardless of the actual treatment received. If a patient is randomized based on an incorrect stratum, then this patient will be analyzed according to the stratum to which the patient should have been assigned per the electronic data capture system, instead of the stratum per the randomization system of IWRS.

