8.1 PRIMARY EFFICACY PARAMETER

The primary efficacy parameter will be the change from baseline to Day 21 in MADRS total score for the mITT population. The MADRS total score is the sum of the 10 individual items. If more than 2 items are missing, then the total score will be set to missing. If there are multiple assessments of MADRS total score for the same nominal visit of a patient, only the last assessment will be used in the analysis.

The primary efficacy parameter will be analyzed using a mixed model for repeated measures (MMRM) with treatment group, pooled study center, visit, placebo responder status at Day 7, and treatment group-by-visit interaction as the fixed effects, and Day 0 MADRS total score, baseline MADRS total score, Day 0 MADRS total score-by-visit and baseline MADRS total score-by-visit interactions as covariates. An unstructured covariance matrix is used to model the covariance of change in scores within patients. The Kenward-Roger approximation will be used to estimate denominator degrees of freedom ([Kenward et al, 1997](#)). The analysis will be performed based on all post-randomization data using only the observed cases without imputation of missing values.

In the case that the MMRM model with unstructured covariance fails to converge with the default algorithm, then the Fisher scoring algorithm will be used to provide better initial values of the covariance parameters; if the model still does not converge, a simplified model without term for study center will be used to find the initial values of the covariance parameters. In the rare event that the model still does not converge after using those initial values, simplified covariance structures will be used to fit the model in the following order until the model converges: (1) ante-dependence, (2) heterogeneous autoregressive, (3) Toeplitz, and (4) compound symmetry.

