8.2 KEY SECONDARY EFFICACY PARAMETERS

[figure not shown]
There are 3 key secondary efficacy parameters as listed below:

[figure not shown]
1. Change from baseline to Day 8 (1 Day after the first randomized treatment) in MADRS total score for mITT population
2. Change from baseline to Day 21 in MADRS total score for the placebo non-responders of mITT population
3. Change from baseline to Day 8 in MADRS total score for the placebo non-responders of mITT population

The key secondary parameters will be analyzed using the same MMRM model as for the primary efficacy parameter, except the placebo responder status at Day 7 will be excluded for the analyses of the 2nd and 3rd key secondary efficacy parameters listed above. A sequential testing procedure will be used to control the overall type I error rate at 5% for the comparisons of between-treatment difference of multiple secondary efficacy parameters in the order listed above. Specifically, the change from baseline to Day 8 in MADRS total score for the mITT population will be tested first at the significance level of 0.05. If the between-treatment comparison is statistically significant, then the analysis of 2nd and 3rd key efficacy parameters for the placebo non-responders will be performed at the same significance level sequentially as long as the treatment effect is statistically significant in the preceding testing.

Plots of fitted (least squares) mean values and their standard errors based on the MMRM model for the change in MADRS total score will be presented by treatment group and by visit.

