12.0 DETERMINATION OF SAMPLE SIZE

The originally proposed primary efficacy variable is the change from baseline (ie., Day 7) at Day 8 in MADRS total score and the primary analysis population included the subset of patients who were placebo non-responders during the placebo lead-in period before randomization. Based on that the study was planned to randomize 700 patients (including both placebo responders and placebo non-responders), assuming standard deviation (SD) of 10 points, which provides 99% power to detect a difference of 3.25 points in MADRS total score between rapastinel 450 mg and placebo at a 2-sided significance level of 0.05.

While the study was ongoing, the primary efficacy variable was revised to be the change from baseline in MADRS score at the last visit, Day 21, and the primary efficacy study population was revised to include all randomized patients (placebo responders and placebo non-responders) based on the feedback by the FDA, EMA, and PDMA. Both of these changes were included in Amendment 2 of the protocol. At the same time of Amendment 2, a blinded data review was conducted for Studies RAP-MD-01, RAP-MD-02, and RAP-MD-03. The pooled SD for the three studies were 7.4, 8.0, and 8.7, respectively, all smaller than the originally assumed 10 points. Sample size was re-calculated using 8.7 as the common SD. The calculation used MMRM model with simulations; it also assumed correlation of 0.5 between the repeated measures and a common drop-out rate of 10% during the randomized treatment period and an additional 5% drop-out rate during the placebo lead-in period for all treatment groups. To have 90% power, the total sample size required is 360 patients. However, the study had already enrolled more than 390 patients with less than 5% of overall drop-out rate, surpassing the re-estimated sample size of 360 patients. The study enrollment was halted as soon as operationally feasible. The final sample size is approximately 420 patients (210 patients per treatment group).

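### Does the SAP leave open whether placebo-responder status is judged over the whole lead-in or at Day 7 alone?

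*SAP*

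**What the plan says.** SAP 2.0 defines the term: "Placebo responders will be defined by meeting at least 1 of the following criteria at any time point during the 1-week double-blind placebo lead-in". The two criteria are a fall of at least half from the Day 0 MADRS total, or a total of 14 or less. The stratification sentence in the same section refers to responder status ("as placebo non-responder vs. placebo responder) achieved during the end of the placebo lead-in period").

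The primary model in SAP 8.1 includes "placebo responder status at Day 7" as a fixed effect. SAP 8.2 says that "the placebo responder status at Day 7 will be excluded for the analyses of the 2nd and 3rd key secondary efficacy parameters", because those two analyses use non-responders only.

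Other sections use the term without a visit:
- SAP 5.0 tabulates disposition by "placebo lead-in period responder status".
- SAP 8.0 pools centers on non-responder counts, a small center being "a center with less than 2 placebo non-responder patients in at least 1 treatment group in the mITT Population".
- SAP 12.0 describes the former primary population as "placebo non-responders during the placebo lead-in period before randomization".

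SAP 8.0 also has a rule for stratification errors: "If a patient is randomized based on an incorrect stratum, then this patient will be analyzed according to the stratum" that the electronic data capture record supports, in preference to the stratum held in IWRS.

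**The concern.** Three timing phrases are in use and no sentence says that they mean the same thing. Table 14.1-1 of the SAP gives the lead-in separate windows for Days 1, 4 and 7, and SAP 12.0 uses Day 7 for a single measurement, the baseline score. A programmer could therefore take Day 7 status to mean the Day 7 score alone. A patient who responded at Day 4 and relapsed by Day 7 would then be a responder by the definition and a non-responder in the model.

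The status has several uses: the randomization stratum, a factor in the primary model, the center pooling, the check for a wrong stratum, and the population of the second and third key secondary tests. Those two tests are under alpha control. If the timing really were undefined, their population could be settled after the data had been seen.

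**Working it through.** **1. The passages side by side.**

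| Place in SAP | Use | Timing phrase | Fits a cumulative status? |
|---|---|---|---|
| 2.0, definition | meaning of responder | any lead-in time point | yes, it is the definition |
| 2.0, stratification | stratum | end of the lead-in | yes, all lead-in visits are then complete |
| 5.0 and 12.0 | disposition, former population | the lead-in as a whole | yes |
| 8.0 | pooling, wrong-stratum check | none | yes, takes the defined term |
| 8.1 and 8.2, model | fixed effect | Day 7 | yes, if Day 7 is when the status is final |
| 8.2, second and third tests | population | none | yes, complement of the definition |

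Patients are randomized on completing the lead-in, and Table 14.1-1 sets Day 7 as the date of the first randomized dose. A status that can be met at any lead-in visit is final on that day. Every row can be read with one meaning. The Day-7-score-only reading contradicts the first row.

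**2. The plan's own figures do not depend on the timing.** With 350 per arm, difference 3.25, SD 10 and two-sided 0.05: 3.25 / (10 × √(2/350)) = 3.25 / 0.756 = 4.30; 4.30 − 1.96 = 2.34; power = Φ(2.34) = 0.990, the stated 99%. For the re-estimate with SD 8.7 and 90% power: n per arm = 2 × (1.960 + 1.282)² × 8.7² / 3.25² = 150.6, so 151; 151 / 0.85 = 177.6, so 178; total 356 against the stated 360. The second check assumes that the difference is still 3.25, which the re-estimate does not state. Responder timing enters neither calculation.

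**3. How many patients the readings would separate.** All inputs are assumed: Day 0 mean 31 or 34, SD 4, minimum 25; mean Day 7 change −5, −7 or −9, with 60% of it present at Day 1 and 85% at Day 4; SD of change 7, 8 or 8.7; correlation 0.3 to 0.85. Over 72 combinations, 8% to 41% respond at any time and 5% to 24% at Day 7; 2% to 17% (9 to 71 of 420) differ. If the mean is already flat from Day 1, the difference reaches 25%. A second set of assumptions, with larger placebo responses, gives 5% to 18% (23 to 74 of 420).

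**4. Effect on the analyses.** 420 patients, 1:1, stratified on any-time status. The model is ANCOVA of the Day 7 to Day 21 change on treatment, Day 0 score and Day 7 score, plus status in the full set, with complete data (a simplification of the MMRM).

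| Mean change, SD, correlation, Day 0 mean | Primary SE, any time / Day 7 | Non-responder SE, any time / Day 7 | Non-responder verdicts differ, no effect |
|---|---|---|---|
| −5, 7.0, 0.85, 34 | 0.361 / 0.362 | 0.374 / 0.373 | 1.6% |
| −7, 8.0, 0.5, 32 | 0.666 / 0.675 | 0.766 / 0.732 | 3.1% |
| −7, 8.7, 0.7, 32 | 0.596 / 0.604 | 0.685 / 0.665 | 3.2% |
| −9, 8.7, 0.3, 31 | 0.785 / 0.794 | 1.035 / 0.920 | 4.1% |

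The largest primary change is 0.675 / 0.666 = 1.014. Type I error of the primary comparison is 4.5% to 5.4% under either status. The largest non-responder change is 1.035 / 0.920 = 1.125. The cause is set size: 248 to 388 patients under any-time status and 319 to 397 under Day 7 status. At 3.25 points, SD 8.7 and no dropout, the two-sample formula of step 2 gives power of 93%, 89% and 84% when 20%, 30% and 40% are responders (168, 147 and 126 per arm).

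**5. What a choice after unblinding could gain.** For two tests each at 5%, P(either significant) = (5% + 5% + P(verdicts differ)) / 2. With the last column this gives 5.8%, 6.6%, 6.6% and 7.1%; direct simulation gave 6.0%, 6.7%, 6.7% and 6.5%. So it is about 6% to 7%, but only for the second key secondary test taken in isolation. SAP 8.2 reaches that test only after the first key secondary is significant at 0.05, and protocol 9.7.5.2 puts the primary in the sequence as well. With no effect anywhere, P(second rejected) ≤ P(first rejected) = 5%, whichever set is picked. Inflation would need a real Day 8 effect in all mITT patients, no Day 21 effect in non-responders (59% to 92% of patients in step 3), and a deliberate choice of set after unblinding.

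**The case for a change.** The best case for a change is that the fix costs almost nothing and the ambiguity touches confirmatory tests. Day 7 is a named visit elsewhere in the SAP, so the literal reading is not far-fetched. The wrong-stratum rule needs a known correct stratum to work. In the simulations the two non-responder sets give different verdicts in 0% to 18% of trials at a true effect of 2 points and 0% to 8% at 3.25 points, so the choice of set can decide a test.

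Part of this stands. The wording is looser than it should be, and nothing equates the three phrases. It does not show a missing rule. SAP 2.0 states a definition, and the sections that use the term without a visit inherit it, including the population of the second and third key secondary tests and the wrong-stratum check. The differing verdicts come from analyzing different numbers of patients; neither set is biased. Making the IWRS rule govern would work against SAP 8.0, which puts the stratum supported by the electronic data capture record above the one in IWRS. Finally, the public protocol does not describe the lead-in at all, and the SAP elaborates a Restricted Access Addendum that is not available here. The operational rule may well be there, and its absence from the public documents is not a gap in the plan.

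**Conclusion.** No change to the plan is needed. This is loose wording around a term that SAP 2.0 defines, and an analyst would fill it sensibly: status is met at any lead-in visit, is final at Day 7, and is used for every purpose. Noting that meaning in the programming specifications is ordinary practice and alters no analysis.

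Even the other reading would do little harm. Both statuses are fixed before randomized dosing, so each gives a valid comparison. The primary standard error moves by less than 1.5%, its type I error is 4.5% to 5.4%, and the 360 and 420 patient figures are unaffected. In the non-responder tests precision can move by up to about 13%. The 6% to 7% error rate in step 5 needs a choice after unblinding, and with no effect anywhere the testing sequence holds it to 5%.

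The classification and precision figures rest on assumed lead-in responses, complete data and an ANCOVA in place of the MMRM. The conclusion rests mainly on the definition in SAP 2.0 and on the status being known before randomized treatment. If the restricted addendum stated a Day-7-only rule, the definition would be the sentence out of line, but the tests would still be valid.

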3.0 OBJECTIVES

[figure not shown]
The objectives of this study are to evaluate the efficacy, safety, and tolerability of rapastinel adjunctive to ADT in patients with MDD.

Efficacy Objectives

The “baseline” referred in the following efficacy objectives is defined as the last measurement prior to the first dose of randomized IP.

- **Primary efficacy objective:** To evaluate the efficacy of rapastinel (450 mg IV) versus placebo in the treatment of MDD as an adjunct to ongoing ADT, as measured by the change from baseline to Day 21 in MADRS total score.
- **Key secondary efficacy objectives:**
 - To evaluate the efficacy of rapastinel (450 mg IV) versus placebo in the treatment of MDD as an adjunct to ongoing ADT, as measured by the change from baseline to Day 8 in MADRS total score (1 Day after the first randomized treatment).
 - To evaluate the efficacy of rapastinel (450 mg IV) versus placebo in the treatment of MDD as an adjunct to ongoing ADT, as measured by the change from baseline to Day 21 in MADRS total score for placebo non-responders.
 - To evaluate the efficacy of rapastinel (450 mg IV) versus placebo in the treatment of MDD as an adjunct to ongoing ADT, as measured by the change from baseline to Day 8 in MADRS total score (1 Day after the first randomized treatment) for placebo non-responders.

RESTRICTED

4.0 ANALYSIS POPULATIONS

The following populations will be considered in the statistical analysis of the study.

4.1 ENROLLED POPULATION

The Enrolled Population will consist of all patients who signed informed consent, received a patient identification number, entered into screening and received 1 dose of investigational product (IP) during the double-blind treatment period.

4.2 SAFETY POPULATION

The Safety Population will consist of all patients who were randomized and received at least 1 dose of IP during the randomized treatment period.

4.3 MODIFIED INTENT-TO-TREAT POPULATION

The modified Intent-to-Treat (mITT) Population will consist of all patients who were randomized, received at least 1 dose of IP during the randomized treatment period, and had at least 1 post-randomization assessment of the MADRS total score.

5.0 PATIENT DISPOSITION

The number of patients in the Enrolled, Safety and mITT populations will be summarized by treatment group and by study center.

Screen-failure patients (ie, patients screened but not included in the enrolled population) and their associated reasons for failure to enroll will be tabulated overall for all screened patients.

The number and percentage of patients in the mITT population who complete the randomized treatment period, of patients who prematurely discontinue during the same period and who entered the safety follow-up period will be presented for each treatment group and pooled across treatment groups for placebo lead-in period responders and non-responders both separately and combined. The reasons for premature discontinuation during the randomized treatment period as recorded on the disposition pages of the electronic case report forms (eCRFs) will be summarized by treatment group and placebo lead-in period responder status for the mITT Population.

